5 STATISTICAL ANALYSIS METHODS

5.1 General Considerations

Summary tables will be presented using descriptive summary statistics. For continuous variables, summary statistics will generally include: number of subjects with data, mean, standard deviation, median, and range (minimum and maximum). For categorical variables, this will generally include: number of subjects randomized or dosed, number with data, and the percent of those with data in each category.

Unless otherwise specified, baseline value is defined as the most recent non-missing measurement collected prior to the first dose. Change from baseline will be defined as post-baseline value minus baseline value.

Statistical testing will be performed to assess efficacy endpoints by conducting pairwise comparison between each BIIB054 group and placebo, and no multiplicity will be adjusted. Unless stated otherwise, all the statistical tests will be 2-sided with a statistical significance level of 0.05 .

The statistical software, SAS[®] will be used for all summaries and analyses.

5.1.1 End of Study (EOS) and End of Treatment (EOT)

For subjects who complete the placebo-controlled period of the study, EOS visit is defined as Week 52 visit; for subjects who are early terminated, EOS visit is defined as the scheduled

CONFIDENTIAL

The information contained herein may not be used, disclosed, or published without the written consent of Biogen MA Inc.

follow-up visit after EOT visit. For subjects who complete the treatment, EOT visit is defined as Week 48.

5.1.2 Analysis Population

- **Intent-to-treat (ITT) population:**
The intent-to-treat population is defined as all randomized subjects who received at least one dose of study treatment (BIIB054 or placebo).
- **Per-protocol (PP) population:**
The per-protocol population is defined as a subset of the ITT population who received at least 70% (10 doses) of study treatment (BIIB054 or placebo).
- **Safety population:**
The safety population is defined as all subjects who received at least one dose of study treatment (BIIB054 or placebo).
- **PK population:**
The PK population is defined as all subjects in the ITT population who had at least one measurable BIIB054 concentration in serum [REDACTED].
- **Pharmacodynamic population:**
The pharmacodynamic population is defined as all subjects in the ITT population who had at least one post-baseline pharmacodynamic measurement.
- **Immunogenicity population:**
The analysis population for immunogenicity is defined as all subjects in the safety population.
- [REDACTED]

5.2 Background Characteristics

The summaries in this section will be based on the ITT population. Unless otherwise specified, all the summary tables and listings will be presented by treatment group.

5.2.1 Accounting of Subjects

The summary of subject disposition will include number (%) of subjects randomized, number (%) subjects randomized but not dosed, number (%) of subjects who completed the treatment/study, and number (%) of subjects who discontinued treatment and/or withdrew from study. For subjects who discontinued treatment and/or withdrew from study, the reasons for discontinuation and/or withdrawal, and days on treatment and days on study will be summarized and listed. The pattern (time and rate) of treatment discontinuation and study

withdrawal will be displayed by Kaplan-Meier plot. The number of subjects in each analysis population will be summarized.

In addition, number of subjects dosed and number of subjects who completed the treatment/study will be summarized by country (region) and site.

The categorization of region is based not only on consideration of geography but also on type of health care system and access to health care in each country. The categories for regions will be:

- Region 1: United States (US);
- Region 2: European countries (including Austria, France, Germany, Israel, Italy, Poland, Spain and United Kingdom) and Canada.

5.2.2 Demographics and Baseline Characteristics

Demographic data, including age (in years), age category (40-50, 51-60, 61-70, 71-80 years), gender, race, ethnicity, height, weight, body mass index (BMI), country (region) and year of education at baseline will be summarized by treatment groups and overall.

Baseline PD history will be summarized by treatment groups and overall, using descriptive statistics. Time since onset of PD symptoms (in years), time since PD diagnosis (in years), subtype of PD (PIGD, TD or indeterminate), side predominately affected at disease onset, symptoms presented at PD diagnosis and immediate family with a history of Parkinson's Disease will be summarized. MDS-UPDRS total and subtotal scores, PIGD, TD, and LE subscore, Hoehn and Yahr stage, [REDACTED] will be summarized. DaT/SPECT imaging outcomes, [REDACTED] outcomes will also be summarized. Baseline MDS-UPDRS score is defined as the Day 1 visit, if Day 1 visit score is not available, screening visit will be used. Baseline PD history data will be listed.

Number (%) of subjects with any PD treatment history will be summarized by treatment groups and overall. Total duration of previous therapies and reason for stopping therapies will be summarized. Number (%) of subjects who had taken MAO-B inhibitors, Dopamine Agonist, Levodopa and other PD medications will be displayed by treatment groups and overall. A listing of PD treatment history will be generated.

Medical history will be coded using the Medical Dictionary for Regulatory Activities (MedDRA). The number (%) of subjects with history (including both ongoing and not ongoing medical conditions) will be summarized by system organ class and preferred term, and by preferred term only. A listing of medical history will be generated.

5.2.3 Concomitant Medications and Non-drug Therapies

All concomitant medications will be coded using the World Health Organization (WHO) medication dictionary. All concomitant non-drug therapies will be coded using the MedDRA dictionary. A concomitant medication/therapy will be defined as any therapy that was taken

	Statistical Analysis Plan Placebo-Controlled Period	V1.0
---	--	-------------

on or after the day of the first dose of study drug. This include therapies that start prior to the initiation of the first dose if their use continues on or after the date of first dose. To determine whether medications and/or non-drug therapies with missing start or stop dates are concomitant with study treatment, the following additional criteria will be used:

- If both the start and stop dates of a therapy are missing, then the therapy will be considered concomitant;
- If the start date is missing and the stop date of the therapy falls on/after the first dose date, then the therapy will be considered concomitant;
- If the start date is missing and the stop date of the therapy falls before the first dose date, then the therapy will be considered non-concomitant;
- If the start date of a therapy is prior to the date of the first dose and the stop date of the therapy is missing and the therapy is listed as ongoing, that therapy will be considered concomitant;
- If the start date of a therapy is prior to the date of first dose and the stop date of that therapy is missing and the therapy is not listed as ongoing, that therapy will be considered non-concomitant.
- If the start date of a therapy is on/after the date of first dose but in the treatment period (last dosing date+28 days) and the stop date of that therapy is missing, then that therapy will be considered concomitant.
- If the start date of a therapy is on/after the treatment period (last dosing date+28 days) and the stop date of that therapy is missing, then that therapy will be considered non-concomitant.

For a record with a partial start/end date, the year/month of the partial date will be compared to that of the date of first dose to determine whether it is concomitant.

The number and percent of subjects taking concomitant medication and non-drug treatments will be summarized by treatment group and overall. Concomitant PD medication will be summarized separately from the other concomitant medication.

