5.3.2 MDS-UPDRS

5.3.2.1 Primary efficacy endpoint

Estimand:

The estimand of the primary analysis is the mean difference of the change from baseline in MDS-UPDRS I+II+III total score at Week 52 between treatment groups in the ITT population in a hypothetical setting where subjects do not start PD medication. MDS-UPDRS data collected after the intercurrent events, i.e., subjects start PD medication will be excluded in the primary analysis. Specifically, the estimand takes the following into consideration:

- A. Population: ITT population as defined in Section 5.1.2
- B. Variable: change from baseline to Week 52 in MDS-UPDRS score
- C. Intercurrent events: had PD medication not been made available to subjects prior to Week 52
- D. Population-level summary: difference in variable means between treatment conditions.

CONFIDENTIAL

The information contained herein may not be used, disclosed, or published without the written consent of Biogen MA Inc.

MMRM will be used as the primary analysis to analyze the change from baseline in MDS-UPDRS score. The model includes the fixed effects of treatment group, time (categorical), baseline PD subtype (categorical; PIGD vs TD vs indeterminate), prior use of PD medication (categorical), treatment group-by-time interaction, region (categorical), baseline MDS-UPDRS I+II+III total (continuous), baseline MDS-UPDRS I+II+III total by time interaction and baseline striatum SBR values (continuous), and baseline striatum SBR by time interaction. A random intercept and slope will be included in the model to model the random effects within subjects. If small sample size in subgroups of PD types causes lack of model convergence, the indeterminate group will be combined with the TD group. The Kenward-Roger approximation will be used to estimate the denominator degrees of freedom. Least square means (LSmeans) of each treatment group as well as treatment difference between BIIB054 groups and placebo will be displayed with 95% CI and p-value at Week 52. If the distribution of the outcome is highly skewed, p-value will be generated from the MMRM model based on ranked data. In the primary analysis, missing data are assumed to be missing at random (Rubin 1976), and MDS-UPDRS I+II+III score is impacted by PD medication.

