4.2.3 Concomitant Medications and Non-Drug Therapies

All medications will be coded using the World Health Organization Drug (WHODrug March 2020 B3 or higher) dictionary. All non-drug therapies (defined as diagnostic procedures or medical treatment procedures) will be coded using the MedDRA dictionary version 23.0 or higher.

The number (%) of subjects taking concomitant general medication (excluding PD medications) and non-drug therapies in the DBE period will be summarized by DBE treatment group for subjects enrolled in the DBE period. In addition, number of subjects in the ITT population that have taken any concomitant medications in the active treatment (placebo-controlled and DBE) period will be summarized. Concomitant non-PD medications and non-drug therapies will be listed in the placebo-controlled and DBE treatment period. Start and stop day in the listing will be computed based on the placebo-controlled baseline.

For subjects enrolled in the DBE period, the number (%) of subjects taking any concomitant PD symptomatic medications, number of subjects taking Dopamine, MAO-B inhibitor, Dopamine Agonist at the baseline of the placebo-controlled period and at the baseline of DBE period will be summarized respectively by DBE treatment group. The placebo-controlled and DBE period data will be summarized in the same fashion. Concomitant PD symptomatic medication will be listed for all subjects in the placebo-controlled and DBE periods. Start and stop day in the listing will be computed based on the placebo-controlled baseline. Please refer to the placebo-controlled SAP for definitions of concomitant therapies and PD symptomatic medication use at baseline.

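### The missing-stop-date rule in Section 5.2.3 contradicts the definition of a concomitant therapy and leaves some continuing PD medication out of the by-arm PD medication table

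*SAP*

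**What the plan says.** The general definition in Section 5.2.3 of the Year 1 SAP begins "A concomitant medication/therapy will be defined as any therapy that was taken"; its only time condition is that use falls "on or after the day of the first dose of study drug". It sets a lower time bound and no upper one.

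A list of extra rules follows for incomplete dates: "To determine whether medications and/or non-drug therapies with missing start or stop dates are concomitant with study treatment, the following additional criteria will be used". Two of them concern therapies started after first dose with no stop date:

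- Counted as concomitant, by this wording: "If the start date of a therapy is on/after the date of first dose but in the treatment period (last dosing date+28 days".
- Not counted as concomitant, by this wording: "If the start date of a therapy is on/after the treatment period (last dosing date+28 days) and the stop date of that therapy is missing".

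A bullet for therapies started before first dose shows that an ongoing therapy is one kind of missing stop date: "the stop date of the therapy is missing and the therapy is listed as ongoing". The last bullet makes no exception for ongoing therapies or for PD medication. The section ends by requiring a separate summary of concomitant PD medication, with concomitant medications summarised by treatment group and overall.

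Section 5.3.2.1 makes the start of PD medication the intercurrent event of the primary estimand: "had PD medication not been made available to subjects prior to Week 52". Section 4.2.3 of the extension SAP takes over the same definition: "Please refer to the placebo-controlled SAP for definitions of concomitant therapies and PD symptomatic medication use at baseline".

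**The concern.** The definition and the last bullet give different answers for the same therapy. The upper limit applies only when no stop date is recorded, so the class turns on whether the therapy was later stopped. Nothing in the definition makes that relevant.

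The rule is most likely to catch PD medication. If such treatment is usually continued once started (my assumption), its record will usually lack a stop date when the data are cut. In a subject who stopped infusions early but is still followed, PD medication started after the cutoff and continued is then not counted. The by-arm concomitant PD medication table would under-report the event on which the Week 52 estimand is built. If arms differ in how many subjects stop infusions early, the under-reporting would also differ between arms.

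**Working it through.** The SAP gives no figure to reproduce. The check applies the rules as written and then compares the cutoff with the end of Year 1.

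**Inputs**
- General definition and missing-date bullets: Year 1 SAP, Section 5.2.3.
- Infusions every 4 weeks, 13 in Year 1, the last at Week 48: Sections 3.1 and 3.1.1.
- EOS is the Week 52 visit for subjects who complete the placebo-controlled period. For subjects terminated early it is the scheduled follow-up visit after EOT: Section 5.1.1.
- Stopping treatment and withdrawing from the study are summarised as separate events: Section 5.2.1.

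**Step 1. Same start day, with and without a stop date**

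| Start, days after last infusion | Stop date missing | Stop date recorded |
|---|---|---|
| 27 | concomitant | concomitant |
| 28 | can meet both of the last two bullets | concomitant |
| 29 | non-concomitant | concomitant |
| 56 | non-concomitant | concomitant |

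The right-hand column follows from the general definition, which is all that applies once both dates are known. At day 28 one bullet covers starts in the treatment period and the next covers starts on or after its end, so the class is unclear.

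**Step 2. An example**

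Last infusion at Week 12, so the cutoff is 12 + 4 = Week 16. PD medication starts at Week 24. If it is stopped at Week 40, it is concomitant. If it is still in use, it is non-concomitant.

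**Step 3. Where the cutoff falls**

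Cutoff week = week of last infusion + 4. Weeks lost before Week 52 = 52 − cutoff week.

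| Last infusion (week) | Cutoff (week) | Weeks lost before Week 52 |
|---|---|---|
| 12 | 16 | 36 |
| 24 | 28 | 24 |
| 36 | 40 | 12 |
| 44 | 48 | 4 |
| 48 | 52 | 0 |

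In days, for a subject given all 13 infusions: 48 × 7 + 28 = 364 = 52 × 7. The cutoff then coincides with the nominal end of Year 1. Section 4.6.3 of the extension SAP allows Week 52 assessments to be delayed by up to 4 weeks, so a short stretch could still be lost in such a subject.

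The right-hand column assumes follow-up to Week 52. If the subject's EOS comes earlier, the lost stretch ends there.

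**The case against.** **An on-treatment window may be intended.** The cutoff is one dosing interval after the last infusion, the section calls that span the treatment period, and the rules decide what is concomitant with study treatment. An earlier cutoff for early stoppers could then be deliberate. As a guess at intent this is fair. It does not remove the contradiction, because therapies with a recorded stop date carry no such limit. Either reading needs a correction.

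**The primary analysis.** A reader might infer that post-medication scores stay in the primary analysis. The documents do not support this. Section 5.3.2.1 excludes data according to the start of PD medication and makes no reference to the concomitant flag.

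**Other reporting of the same event.** A reader might infer that an arm with more discontinuations will appear, across the report, to need less PD medication. That goes too far. Section 5.3.2.8 plans a subgroup analysis of time to start of PD medication, so the event is also handled as an outcome in its own right, and text between Sections 5.3.2.4 and 5.3.2.8 is redacted. Only the concomitant PD medication table is shown to be affected.

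**Size.** It is tempting to use the 10% Week 52 dropout rate from Section 4 to estimate how many subjects are affected. That rate removes subjects from the Week 52 sample size. The subjects at issue here stop infusions and are still followed, which is a different group. The SAP does not give their number or how long they are followed, and this may be left to the protocol. The number could be very small.

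**Conclusion.** The point holds as an internal contradiction in Section 5.2.3 that makes one descriptive table wrong if the rule is followed as written. Therapies started after last dose plus 28 days are counted if they have a stop date and dropped if they are continuing. A start exactly at the cutoff has no clear class.

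The loss is confined to subjects followed beyond their own cutoff. It is up to 36 weeks of therapy starts for a last infusion at Week 12 and falls to none, or close to none, for a subject given all 13 infusions. The number of subjects affected cannot be derived from the SAP. That PD medication would often fall under the rule rests on the assumption that it is usually continued once started.

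The point is still worth correcting, because the table describes the intercurrent event of the Week 52 estimand by arm and because the extension SAP inherits the definition. The primary estimate and its test are not affected.

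**What to change.** Apply one window to every therapy, whether or not a stop date is recorded: concomitant if taken at any time from first dose to the subject's EOS as defined in Section 5.1.1. Remove the last-dose-plus-28-days condition from the missing-stop-date bullets. This also settles the overlap at day 28.

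At a minimum, count every PD medication start up to the subject's EOS in the PD medication table, so that it agrees with the analysis of time to start of PD medication.

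If an on-treatment summary is also wanted for other drugs, apply the same cutoff to therapies with and without a stop date, and label the table accordingly.

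The cost is a change of wording and one line in the derivation, with no new data. The downside is small: some therapies started after treatment ended will enter the table.

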5.2.4 Protocol Deviations

Protocol deviations identified during site monitoring will be captured in a Protocol Deviation log and categorized as major or minor deviations. The major protocol deviations will be summarized and listed. The minor protocol deviations will also be listed. Number (%) of subjects with at least one major deviation will be summarized by category. The protocol deviation related to COVID-19 will be listed.

5.2.5 Study Drug Exposure and Study Drug Compliance

The number of infusions administered will be summarized as both continuous and category variables (categories as integers from 1 to 13, and 1-3, 4-6, 7-9, 10-13). The number of weeks on study drug, calculated as $(\text{date of last dose} - \text{date of first dose} + 1) / 7$, will be summarized

CONFIDENTIAL

The information contained herein may not be used, disclosed, or published without the written consent of Biogen MA Inc.

as a categorical variable (every 8 weeks from 0 to ≥ 48 Weeks) as well as a continuous variable. Overall compliance, which is the percentage of drug infusions actually received over 13 planned doses, will be summarized regardless of study completion for all subjects. Percentage of study treatment taken up to the last dose, calculated as (the actual number of infusions / the number of infusions a subject is expected to take until the date of last infusion), will be summarized as a continuous variable. This table will be presented by treatment group. For subjects who completed study, the number of expected infusions is 13. For subjects who withdrew from study early, the number of expected infusions is the planned number of infusions before the time of withdrawal.

A listing of study drug administration records, including infusion start date and time, infusion stop date and time, total volume prepared, total volume administered, location of infusion, initial infusion rate, dose interruption or rate change or not, time of interruption or rate change, infusion rate after interruption or rate of change, reason for interruption or rate change will be provided.

5.3 Efficacy Endpoints

5.3.1 General Consideration

Clinical efficacy (clinical function) Assessments include Movement Disorder Society Sponsored Revision of the Unified Parkinson's Disease Rating Scale (MDS-UPDRS), [REDACTED]

[REDACTED]

[REDACTED] The questionnaire as well as the scoring algorithm for all these clinical assessments are described in Appendix I.

Unless otherwise noted, the analysis will be performed based on all the subjects in both Cohort A and B and the common visits. For numerical outcomes, the actual value and the change from baseline will be presented by treatment group and visit. For categorical outcome, the count and frequency will be summarized by treatment group and visit.

Analysis population

All clinical function endpoints will be evaluated in the ITT population as defined in Section 5.1.2. MDS-UPDRS [REDACTED] may also be analyzed in the per protocol population as defined in Section 5.1.2.

Baseline value

MDS-UPDRS, [REDACTED] are assessed at both screening visit and Day 1 visit. [REDACTED]

CONFIDENTIAL

The information contained herein may not be used, disclosed, or published without the written consent of Biogen MA Inc.

██████████. For all of them, the baseline values are defined as the latest data collected prior to or on the first dose date.

Visit windows for mapping clinical function endpoint

Assessments from all scheduled visits, EOT visit and EOS visit, and unscheduled visits will be mapped to an appropriate analysis visit using a windowing scheme (Appendix II).

Handling missingness of itemed question score

For MDS-UPDRS, the maximum number of missing item allowable to provide a valid standard score for each part are: 2 for Part I, 2 for Part II, 9 for Part III, and 0 for Part IV. For each part, if no item is missing, the total score is the sum of all the item scores in the part. If some items are missing, the total score is the sum of all available item scores multiplied by the total number of items in the part and then divided by the number of items with available scores. MDS-UPDRS Part I+II+III (II+III) total score is the sum of all relevant part scores. As subjects were not guided to enter 0 to the Part IV questionnaire before they start symptomatic PD medication, some subjects left blank to the Part IV items at applicable visits. Therefore, we will impute the missing item in Part IV as 0. The total score is missing if and only if any relevant part score is missing (Stebbins et. al. 2015). For all other clinical endpoints, if more than half of the items are missing, then the total score is set to be missing. Otherwise, the missing item score will be imputed and used to derive the total score. In particular, if an item score is missing at a post baseline visit, it will be imputed by last observation carried forward method. And if an item score is missing at baseline, it will be imputed by the median of the item score among all the subjects of the same PD subtype (PIGD-dominant, Tremor-dominant, Indeterminate) in the study who have a baseline score in the item.

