5.3.3 Other clinical efficacy endpoints

Other clinical efficacy (function) and quality of life assessments are listed as below. The questionnaire as well as the scoring algorithm for these clinical assessments are described in Appendix I.

- [REDACTED]
- [REDACTED]
- [REDACTED]
- [REDACTED]
- [REDACTED]
- [REDACTED]
- [REDACTED]
- [REDACTED]
- [REDACTED]
- [REDACTED]
- [REDACTED]
- [REDACTED]
- [REDACTED]
- [REDACTED]
- [REDACTED]
- Clinical Global Impressions Improvement (CGI-I) Scale (collected at Week 52 in the US sites only)*,
- Patient Global Impression of Change (PGI-C) (collected at Week 52 in the US sites only)*.

Data after PD medication will be included in the analysis for all the outcomes except [REDACTED].

For each clinical assessments that are collected longitudinally, an MMRM model will be used to analyze the change from baseline in the continuous clinical outcome, with addition of adjustment for the corresponding baseline outcome value and its interaction with time. i.e. the model will include fixed effects of treatment group (categorical), time (categorical), region (categorical), treatment group-by-time interaction, baseline value of the corresponding outcome (continuous), baseline value of the outcome by time interaction, baseline MDS-UPDRS I+II+III total score (continuous), baseline MDS-UPDRS I+II+III total score-by-time interaction, baseline striatum SBR values (continuous), and baseline striatum SBR by time interaction. The endpoints listed with a “*” next to them, will additionally include the baseline PD subtype (categorical) as a covariate. An unstructured covariance matrix will be used to model the within-subject variance-covariance errors. If the unstructured covariance structure matrix results in a lack of convergence, the heterogeneous Toeplitz covariance structure followed by the heterogeneous first-order autoregressive covariance structure will

CONFIDENTIAL

The information contained herein may not be used, disclosed, or published without the written consent of Biogen MA Inc.

be used. Least square means (LSmeans) of each treatment group as well as treatment difference between BIIB054 groups and placebo will be displayed with 95% CI and p-value at Week 52.

For CGI-I and PGI-C that are only collected at Week 52, an ANCOVA model will be used to analyze the data and adjust for the covariates of baseline MDS-UPDRS I+II+III (continuous) and baseline striatum SBR values (continuous), and baseline PD subtype (categorical).

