4.3 Efficacy analyses

4.3.1 General Consideration

The analysis population for the efficacy analyses are defined in Section 4.2.1. The analysis period includes data from both placebo-controlled and DBE period combined. That is, data from both the placebo-controlled and DBE periods will be included in the analysis.

The following three comparisons will be evaluated for the long-term efficacy analyses of BIIB054:

- The early start 250 mg compared with the pooled delayed start group;
- The early start 1250 mg compared with the pooled delayed start group;
- The early start 3500 mg compared with the pooled delayed start group

The following comparisons may also be evaluated:

- The early start 250 mg compared with the delayed start 250 mg;

CONFIDENTIAL

The information contained herein may not be used, disclosed, or published without the written consent of Biogen MA Inc.

	Statistical Analysis Plan Dose Blinded Extension Period	V2.0
---	--	-------------

- The early start 1250 mg compared with the delayed start 1250 mg.
- The early start 3500 mg compared with the delayed start 3500 mg.

The pooled delayed start group contains all the subjects who were randomized to placebo treatment in the placebo-controlled period including those who did and who did not enter into the DBE period. There will be no multiple comparison adjustments. Data after subjects start PD symptomatic treatment will be included in the analyses, since the majority of subjects are expected to take PD medication after Week 52.

Subjects who were randomized to placebo group but accidentally received one or more doses of the active treatment during the placebo-controlled period will be classified as delayed start for all the efficacy, pharmacodynamic, and ██████ analyses.

Visit Windows for by visit analyses

For the by visit summaries and MMRM models, the analysis visit should be defined using visit windows (see Tables 6-16 in the Appendix). If there is more than 1 value in the same analysis visit window (>1 value for the same analysis visit) for a certain parameter for a subject, then the closest record to the target visit day will be used for the by visit analysis. If they are with the same distance from the target visit day, then the record with the later time will be used for the by visit analysis.

Handling of missing items for scales

Please refer to the placebo-controlled SAP for the imputation method. The same method will be applied to efficacy endpoints collected in the DBE period.

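### Item-level LOCF for up to half of a non-MDS-UPDRS scale understates change in affected scores and can distort treatment differences in either direction

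*SAP*

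**What the plan says.** Section 5.3.1 of the placebo-controlled SAP (Handling missingness of itemed question score) sets two rules in one paragraph.

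- **MDS-UPDRS Parts I to III.** Within stated caps on missing items, "the total score is the sum of all available item scores multiplied by the total number of items in the part", divided by the number of items answered. The fill therefore comes from the same visit.
- **Everything else.** "For all other clinical endpoints, if more than half of the items are missing, then the total score is set to be missing". Then: "Otherwise, the missing item score will be imputed and used to derive the total score". After baseline, "if an item score is missing at a post baseline visit, it will be imputed by last observation carried forward method". For baseline the rule reads: "if an item score is missing at baseline, it will be imputed by the median of the item score among all the subjects". That median is restricted to people who share the subject's PD subtype and answered the item at baseline.

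Section 5.3.3 analyses the other longitudinal scales by MMRM on change from baseline. On symptomatic treatment it says: "Data after PD medication will be included in the analysis for all the outcomes except" a redacted item. Section 4.3.1 of the DBE SAP refers back for missing items: "The same method will be applied to efficacy endpoints collected in the DBE period". The visible text gives no reason for treating the two groups of scales differently, no limit on how far a value may be carried, no expected item-missing rate and no sensitivity analysis for this rule.

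**The concern.** In a progressive disease, a carried item contributes no change after the visit at which it was last answered. The total built from it understates the subject's change, yet enters the MMRM as if fully observed.

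The effect on the treatment comparison depends on how item missingness falls across arms. Similar missingness pulls the difference toward zero; unequal missingness can enlarge it or produce one where none exists. The rule is therefore not reliably conservative.

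The extension adds a further problem. Placebo subjects switch to BIIB054 at Week 52 (DBE SAP 2.1.2), and data after PD medication are kept (DBE SAP 4.3.1). Nothing in the rule stops an item answered on placebo, or before symptomatic medication, from being carried into a score that is meant to describe the subject afterwards.

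**Working it through.** The plan gives no figure for these scales to reproduce. Its power figures of about 80%, 73% and 89% concern MDS-UPDRS I+II+III, which this rule does not touch.

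**Inputs.** The ceiling of half the items comes from 5.3.1. The 55% reduction comes from section 4, where it is stated for MDS-UPDRS; it is borrowed here only as an illustrative ratio. Linear progression, equally weighted items, the carry weeks and the missing shares are assumptions.

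**1. Loss in one affected score.** With m of k items last answered at week s and scored at week t, loss = (m/k)(1 − s/t). For half the items:

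- Week 24 to Week 52: 0.5 × (1 − 24/52) = 27%
- Week 40 to Week 52: 0.5 × (1 − 40/52) = 12%
- Week 48 to Week 52: 0.5 × (1 − 48/52) = 4%
- Week 24 to Week 72: 0.5 × (1 − 24/72) = 33%
- An observed baseline value carried to any later visit: 50%

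**2. Trial level, equal missingness in all arms.** If a share q of subjects is affected, the retained share of both the change and the difference is 1 − q(m/k)(1 − s/t). With half the items missing in those subjects:

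- q = 20%: 1 − 0.2 × 0.5 = 90% (baseline carried), to 99% (Week 48 carried)
- q = 5%: 1 − 0.05 × 0.5 = 97.5%, to 99.8%

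**3. Trial level, unequal missingness.** Set placebo change to 1 and active change to 0.45, so the true difference is 0.55. Let p and a be the overall shares of items missing on placebo and active, with baseline carried. The estimated difference is (1 − p) − 0.45(1 − a).

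- p = 0%, a = 20%: 1 − 0.36 = 0.64, or 116% of the truth
- p = 10%, a = 30%: 0.90 − 0.315 = 0.585, or 106%
- p = 20%, a = 0%: 0.80 − 0.45 = 0.35, or 64%
- p = 30%, a = 10%: 0.70 − 0.405 = 0.295, or 54%
- No true effect, p = 10%, a = 30%: 0.90 − 0.70 = 0.20, a spurious difference of 20% of the placebo change (11% if Week 24 is carried, since 0.20 × (1 − 24/52) = 0.108)

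**4. LOCF against prorated change.** This was simulated for an assumed 20-item scale scored 0 to 4, with a 55% slower slope on active and Week 52 items missing at random. Carrying Week 24 items kept 94%, 86% and 73% of the full-data difference at 10%, 25% and 50% of items missing; change over the answered items, scaled up, kept about 100%.

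Error per score (RMSE against the complete score) depends on the age of the carried value. From Week 24, prorated change was slightly better: 0.90 v 0.95, 1.56 v 1.71 and 2.70 v 2.85. In a separate run with half the items missing, LOCF was better when the value was recent: 2.20 (Week 40) or 1.99 (Week 48) against 2.75 for prorated change.

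**The case against.** The strongest reply is that the consequence is limited. The primary and secondary efficacy endpoints are MDS-UPDRS scores, so no alpha-controlled test is involved. Half the items is a permitted ceiling, not an expectation. The two scales left visible in the 5.3.3 list, CGI-I and PGI-C, are collected only at Week 52 and have no earlier value to carry. EP-RPS is built from MDS-UPDRS Part III and has its own interpolation rule in Appendix IV. The longitudinal multi-item scales are redacted, and their scoring algorithms sit in Appendix I, which is not at hand. Prorated scores also enter the MMRM as if observed. All of this stands and limits the point to non-primary scales.

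A reader might infer more than the documents support:

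- **That differences always shrink.** Step 3 of the working shows otherwise. The baseline median does not freeze anything by itself either: for an assumed skewed 0 to 4 item with mean 0.75 and median 0, it shifts that item's change by +0.75 on average.
- **That an item never answered shows zero change throughout.** The SAP does not say whether an imputed baseline value counts as an observation to carry. It is silent on what happens when no earlier observed value exists.
- **That the subject's own screening item is available and ignored.** The only visible scale said in 5.3.1 to be among those that "are assessed at both screening visit and Day 1 visit" is MDS-UPDRS, which is exempt from this rule. Moreover, the general baseline definition in 5.1 takes the latest non-missing pre-dose measurement, which, read item by item, could already use a screening value.

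**Conclusion.** The point holds for multi-item longitudinal scales other than MDS-UPDRS. The plan uses unlimited item LOCF for up to half of a scale, where the same paragraph chose same-visit proration for MDS-UPDRS, and it gives no reason. Following it understates change in an affected score, by 27% in the Week 24 to Week 52 example and by 4% when the value comes from Week 48, assuming linear progression and equally weighted items. The bias in the treatment difference is toward zero only if item missingness is similar across arms.

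The size for the trial cannot be determined. Section 5.3.5 records missed assessments and remote visits during Covid-19, which makes incomplete forms plausible, but neither SAP gives an item-missing rate. If few items are missing, the effect is small. The carry of placebo-period or pre-medication items into later scores is a possibility that the rule leaves open, not an established amount.

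**What to change.** In 5.3.1, and so through DBE SAP 4.3.1, replace item LOCF for these scales unless an instrument's own scoring rule in Appendix I applies; say explicitly that such a rule takes precedence. Compute change over the items answered at both baseline and the visit, multiplied by total items / items answered at both. Keep the existing half-missing limit, applied to that common set. Retain LOCF only as a sensitivity analysis, and state what it carries when no earlier observed value exists. The same-subtype median can remain for the displayed baseline total and the baseline covariate. Report item missingness by arm and visit so that readers can judge the size of the problem.

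The cost is SAP wording and one changed derivation. Three drawbacks should be stated. The method assumes that missing items progress like the answered ones. It is somewhat noisier per score than LOCF when the carried value is recent. And the change no longer equals the difference of two displayed totals, so the definition of change in 5.1 needs an exception and the tables a footnote.
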